## **6.2. Data and Safety Monitoring Board**

An independent DSMB will be established to closely monitor the safety of subjects. The primary mission of the DSMB is to ensure that decisions are made that serve the best interests of patients volunteering for the study.

The independent DSMB will be comprised of 4 voting members: 3 academicians/clinicians with expertise in pulmonary care, critical care, and/or infectious diseases as related to COVID-19 pneumonia, and a statistician. Representatives from the Contract Research Organization (CRO) and Sponsor's Chief Medical Officer will be able to attend the open meetings to provide information and administrative support to the DSMB. However, they will not have any voting rights and will not attend the closed meeting where unblinded data may be discussed.

No SAEs have been associated with the investigational medicinal product. Thus, all SAEs will be considered as unexpected for reporting purposes. All reported deaths and treatment-emergent SAEs will be sent by EastHORN Safety to the DSMB within 2 working days of notification of the CRO/Sponsor by the sites. The events will be evaluated by the DSMB and comments returned to EastHORN Safety within 2 working days of notification of the DSMB. A DSMB meeting does not necessarily need to be convened. Ad hoc meetings will be convened whenever felt appropriate by a DSMB member.

In Part 1, periodic safety reviews will be conducted after 12, 24, 36, and 48 subjects have been fully dosed and completed assessment at Day 14. Only DSMB members will be provided with partially unblinded results separated into 2 groups by treatment without identifying the actual treatment. If all participants have completed study therapy before the last DSMB meeting involving review of 48 subjects after their Day 14 visit can be held, this meeting can be cancelled at the discretion of the DSMB chair.

Data may be further unblinded and/or the study paused at the discretion of the DSMB chair; otherwise, enrollment will continue during the safety review.

Please refer to the DSMB Charter for further details.

## **6.3. Dose Discontinuation Criteria**

Dosing of rhu-pGSN may be stopped during the study at the discretion of the DSMB. In general, doses should not be interrupted for Grade 1 AEs, but treatment to control symptoms should be provided, if applicable.

## **6.4. Management of rhu-pGSN Injection-Related Reactions**

Injection-related reactions (IRRs) ([Table 3](#)) will be defined according to the NCI CTCAE, version 5.0 or higher.

**Table 3: Definition of Injection-Related Reactions**

Adverse Event	Grade 1	Grade 2	Grade 3	Grade 4
IRR	Mild transient reaction; injection interruption not indicated; intervention not indicated	Therapy or injection interruption indicated but responds promptly to symptomatic treatment (e.g., antihistamines, NSAIDS, narcotics, IV fluids); prophylactic medications indicated for d24 hours	Prolonged (i.e., not rapidly responsive to symptomatic medication, brief interruption of injection, or both); recurrence of symptoms following initial improvement; hospitalization indicated for clinical sequelae	Life-threatening consequences; urgent intervention indicated

Abbreviations: IRR=injection-related reaction; IV=intravenous; NSAIDs=non-steroidal anti-inflammatory drugs.

#### Management of Grade 1 IRRs

If a subject presents with a Grade 1 IRR:

- The injection may be continued; however, the rate may be reduced to 50% at the discretion of the Investigator.
- If the symptoms resolve, the injection can be increased, as tolerated, to the baseline rate.
- The subject may receive appropriate further treatment for IRRs if clinically indicated per the site's standard practice for management of IRRs.

#### Management of Grade 2 IRRs

If a subject presents with a Grade 2 IRR:

- The injection should be stopped immediately.
- The subject should receive appropriate further treatment with an antihistamine and/or acetaminophen (paracetamol) if clinically indicated per the site's standard practice for management of IRRs. Further medications can be administered if necessary.
- Once the symptoms have been resolved or reduced to Grade 1, the injection can be continued at an injection rate of 50%.
- If a subject who developed a Grade 2 IRR receives further injections, then premedication following the site's standard practice for premedication for IRR should be given before all subsequent injections of rhu-pGSN given at a rate of 50% of the original rate.

### Management of Grade 3 IRRs

If a subject presents with a Grade 3 IRR:

- The injection should be stopped immediately.
- The subject must receive appropriate treatment with an antihistamine and/or acetaminophen (paracetamol) and/or methylprednisolone (or equivalent) and, if necessary, further medications (i.e., epinephrine, bronchodilator).
- Only after the complete resolution to dGrade 1, and after having received appropriate prophylactic medication(s) as described above, the injection may be resumed at an injection rate of 25%. If, after 20 minutes, the subject's symptoms do not return and vital signs are stable, the injection rate may be increased to a maximum of 50%.
- If, after the resumption of injection, symptoms return (irrespective of grade), the injection must be stopped immediately, and the injection tubing should be disconnected from the subject.
- Subjects experiencing a Grade 3 IRR may only receive further injections of study drug, provided clinically appropriate precautions are undertaken and agreed upon by Investigator and Medical Monitor.

### Management of Grade 4 IRRs

If a subject presents with a Grade 4 IRR:

- The injection should be stopped immediately, and the injection tubing should be disconnected from the subject.
- The subject should receive appropriate treatment with an antihistamine and/or acetaminophen (paracetamol) and/or methylprednisolone (or equivalent) and, if necessary, further medications (i.e., epinephrine, bronchodilator).
- The subject must not receive further injections of rhu-pGSN if rhu-pGSN is judged by the Investigator to be the cause of the IRR.

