## **6.8. Criteria for Treatment Discontinuation**

Subjects are free to discontinue their participation in the study at any time and without prejudice to further treatment. The Investigator must withdraw any subject from the study if that subject requests to be withdrawn, or if it is determined that continuing in the study would result in a significant safety risk to the subject.

The subject's participation in this study may be discontinued for the following reasons:

- Subject withdrew consent
- Unacceptable AE
- Subject is unwilling or unable to continue the study or is lost to follow up
- Subject is non-compliant with study procedures/study protocol
- Investigator decides that withdrawal from the study is in the best interest of the subject
- Any clinically significant change in subject's medical condition (at the discretion of the Investigator)
- Sponsor decision to end the study

If a subject withdraws from the study prematurely, assessments scheduled for the EOS Visit should be performed ASAP. If a subject refuses further assessment, the subject should be contacted for safety evaluations (AE/concomitant medications/potential pregnancy) approximately 28 and 90 days after study withdrawal.

If such withdrawal occurs, or if the subject refuses to participate in the EOS Visit, the Investigator must determine the primary reason for a subject's withdrawal from the study and record the information on the electronic case report form (eCRF). If the reason for withdrawal is an AE, monitoring should continue until the outcome is evident. The specific event or test result(s) must be recorded in the eCRF. At the discretion of the Sponsor, subjects may also be removed from the study.

It should be clearly documented in the source data whether a subject withdrew his/her consent and will not enter the follow-up phase, or if a subject withdrew his/her consent for study drug treatment but will continue further participation in the study.

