### **10.3. Assessment of Causality**

The relationship of each AE to the study drug administration will be assessed by the Investigator after careful consideration of all relevant factors such as (but not limited to) the underlying study indication, coexisting disease, concomitant medication, relevant history, pattern of the AE, temporal relationship to receipt of the study medication and de-challenge or re-challenge according to the following guidelines:

YES (possible, probably or definitely related): there is a reasonable possibility that the study drug caused the event; one or more of the following criteria apply:

- The event follows a reasonable temporal sequence from administration of study drug.
- The event could not be reasonably attributed to the known characteristics of the subject's clinical state, environment or toxic factors or other modes of therapy administered to the subject.
- The event follows a known pattern of response to study drug.
- The event disappears or decreases on cessation or reduction in dose of the study drug. In some situations, an AE will not disappear or decrease in intensity upon discontinuation of the study drug despite other clear indications of relatedness.

NO (probably not related or definitely not related): There is no reasonable possibility that the study drug caused the event and none of the criteria from the previous section apply; one or more of the following criteria apply:

- The event does not follow a reasonable temporal sequence from administration of study drug.
- The event could be reasonably attributed to the known characteristics of the subject's clinical state, concurrent illness, environment or toxic factor or other modes of therapy administered to the subject.
- The event does not follow a known pattern of response to study drug.
- The event does not disappear or decrease on cessation or reduction in dose of the study drug, and it does not reappear or worsen when the study drug is re-administered.

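### After a life-threatening (Grade 4) injection reaction, Protocol 6.4 bars re-dosing only if the Investigator alone judges rhu-pGSN to be the cause; otherwise it omits the Medical Monitor agreement that every Grade 3 reaction needs

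*Protocol*

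**What the plan says.** Protocol Section 6.4 sets out management of injection-related reactions (IRRs) by grade. Table 3 defines Grade 4 as "Life-threatening consequences; urgent intervention indicated". For Grade 4 the injection is stopped, the line is disconnected and the subject is treated. The only sentence about later doses is: "The subject must not receive further injections of rhu-pGSN if rhu-pGSN is judged by the Investigator to be the cause of the IRR".

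The two grades below have rules on later doses that do not depend on cause. After Grade 3, subjects "may only receive further injections of study drug, provided clinically appropriate precautions are undertaken and agreed upon by Investigator and Medical Monitor". After Grade 2, premedication "should be given before all subsequent injections of rhu-pGSN given at a rate of 50% of the original rate".

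Section 10.3 defines relatedness for each adverse event. The YES category covers possible, probable and definite relationships, and one criterion is enough. The first criterion is "The event follows a reasonable temporal sequence from administration of study drug". The NO category requires that "There is no reasonable possibility that the study drug caused the event and none of the criteria from the previous section apply".

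Three general provisions also bear on a subject who has had a Grade 4 reaction:

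- Section 6.3: "Dosing of rhu-pGSN may be stopped during the study at the discretion of the DSMB".
- Section 6.8: the Investigator must withdraw a subject "if it is determined that continuing in the study would result in a significant safety risk to the subject".
- Section 8.4: anaphylaxis precautions apply at every administration.

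The SAP has no re-dosing rule. Its Section 12.10.1.1 only tabulates injection-related events by severity.

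**The concern.** Conditions on re-dosing would be expected to tighten, or at least not loosen, as reactions become more severe. In 6.4 they tighten only if the Investigator names rhu-pGSN as the cause. Otherwise the section is silent on Dose #2 or Dose #3, and the second medical opinion required after a Grade 3 reaction is not required after a life-threatening one.

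Two features make that single judgement a weak gate. Under Section 8.12 the site team is blinded, so by default the Investigator must decide whether rhu-pGSN was responsible without knowing whether rhu-pGSN or saline was given. The subjects also have severe COVID-19, and those in Part 2 are intubated at WHO score 6 or 7, so another explanation for a sudden deterioration may be at hand.

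What is at stake is the safety of an individual subject at the next dose. The statistical inference is not involved.

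**Working it through.** The check is mainly a comparison of text. The documents state no figure to reproduce.

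**Step 1. Conditions by grade (Protocol 6.4).**

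| Reaction | The interrupted injection | Later doses | Depends on cause? | Medical Monitor agreement? |
|---|---|---|---|---|
| Grade 2 | May continue at 50% rate once resolved or Grade 1 | Premedication, 50% rate | No | No |
| Grade 3 | May resume at 25%, then at most 50%, once Grade 1 or lower | Precautions agreed by two parties | No | Yes |
| Grade 4, rhu-pGSN judged the cause | Line disconnected, no resumption step | Barred | Yes | Not needed |
| Grade 4, judged otherwise | Line disconnected, no resumption step | Nothing written | – | No |

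The gap is confined to the last row.

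**Step 2. How a subject reaches the last row.** There are two routes.

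- *Unrelated under 10.3.* NO requires that none of the four YES criteria apply. A reaction during or shortly after an injection will almost always satisfy the timing criterion, so this route is nearly empty.
- *Possibly related under 10.3, but not judged the cause under 6.4.* Section 6.4 does not refer to 10.3 and speaks of the cause in the singular. An Investigator could record a possible relationship and still hold that COVID-19 was the cause. Read literally, 6.4 then bars nothing. How often this happens depends on how Investigators read that wording, and the documents do not settle it.

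**Step 3. Does another provision supply the missing agreement in time?** Sections 6.3, 6.8, 8.4, 8.5, 8.12 and 10.3 and the SAP contain no requirement for Medical Monitor agreement before the next dose after a Grade 4 reaction. There is a per-event route to the DSMB: a life-threatening event is an SAE (10.1.2), is reported within 24 hours of the Investigator's knowledge (10.7), reaches the DSMB within 2 working days of the sites' notification, and is commented on within 2 further working days (6.2).

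Doses are due at 0, 12 and 36 hours, each ±60 minutes (Section 8.1). Taking Dose #1 at time 0:

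- Dose #1 to Dose #2: 12 − 1 = 11 h to 12 + 1 = 13 h.
- Dose #1 to Dose #3: 36 − 1 = 35 h to 36 + 1 = 37 h.
- Dose #2 to Dose #3: 35 − 13 = 22 h to 37 − 11 = 26 h.

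Assume that the Investigator knows of the reaction at once. After a reaction at Dose #1, Dose #2 falls due before the 24-hour reporting limit. Dose #3 falls due after that limit but before 24 hours plus 2 + 2 = 4 working days have passed. After a reaction at Dose #2, Dose #3 falls due at about the reporting limit. These limits are maxima and reports may move faster, but nothing in the protocol holds the next dose until they do.

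**Step 4. Doses at stake.** After a Grade 4 reaction at Dose #1, 3 − 1 = 2 doses remain; at Dose #2, 3 − 2 = 1; at Dose #3, none.

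**The case against.** The strongest reply is that the gap is nearly empty and already covered. Section 10.3 governs every adverse event without needing a cross-reference, and under it almost any reaction at the time of injection is related. The withdrawal duty in 6.8 is mandatory, does not depend on cause and bears directly on the next dose. Section 6.8 also allows discontinuation for an unacceptable event and removal by the Sponsor. The event goes to the DSMB, which may call an ad hoc meeting, and 8.12.1 permits unblinding where it would change management. If another cause is clear, premedication or a slower rate may serve no purpose, and leaving the decision to the bedside physician is defensible.

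Most of this stands, and it is why the point is small. It does not remove the difference between being the cause and being possibly related. Nor does it explain why a second opinion is required at Grade 3 and not here. The 6.8 duty arises only once someone has determined that the risk is significant, and it names no second reviewer.

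A reader might go further and infer that Grade 4 reactions are, overall, less strictly controlled than Grades 2 and 3, for instance by counting the conditions that apply whatever the cause. The documents do not support that. Such a count gives no credit to the strictest rule in the section, an outright ban, and it ignores that the interrupted injection has no resumption step at Grade 4 but may be resumed at Grade 3. A reader might also infer that the subject in the last row of the table is unprotected; 6.3, 6.8, 8.4 and the SAE route show otherwise.

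**Conclusion.** The point holds in a limited form. When a Grade 4 reaction is not judged to be caused by rhu-pGSN, Section 6.4 omits the Medical Monitor agreement that any Grade 3 reaction requires, and its causal wording is stricter than the related standard in 10.3. At most two later doses per subject are exposed to this.

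The conclusion rests on reading 6.4 literally, and on no unpublished pharmacy or safety manual supplying the missing step. The documents give no rate of Grade 4 reactions, so no frequency or level of risk is claimed. Sample size, power and the analyses are not affected. This is a cheap improvement on patient-safety grounds; it is not a flaw that undermines the trial.

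**What to change.** Replace the last Grade 4 bullet in Section 6.4 with a rule to this effect:

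> No further study drug is given if the Investigator considers study drug a possible, probable or definite cause of the IRR. In any other case, further study drug is given only after resolution to Grade 1 or lower, and only with precautions that the Investigator and the Medical Monitor have agreed before the next dose.

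This matches the causal test to 10.3, carries over the Grade 3 second opinion, and refers to study drug, which a blinded Investigator can apply to either arm.

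The cost is one bullet and, rarely, a missed or late dose. A subject who misses a dose leaves the per-protocol set, which needs all three doses (Protocol 11.1, SAP 10.6), but stays in the FAS, which needs one (Protocol 11.3, SAP 10.4).

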## **6.5. Study Duration**

Subjects will be treated with 3 doses over 36 hours: after the initial dose is administered (Dose #1), then next dose (Dose #2) is administered 12 hours later, and the last dose is administered 24 hours later (Dose #3 administered 36 hours after Dose #1).

Subject screening will occur for Part 1 within 24 hours of determination of WHO severity score of 4 to 6, whether the severity score is attained on admission or during current ongoing hospitalization, or for Part 2, within 24 hours of intubation without ECMO with a WHO severity score of 6 or 7. Eligible subjects will be randomized within 12 hours of informed consent (Part 1) or 24 hours of intubation (Part 2), and dosed within 12 hours of randomization (both parts).

Subjects are followed for safety and efficacy through Day 90.

## **6.6. Total Duration of Subject Participation**

Subjects will be observed for the primary efficacy endpoint with daily assessments (including WHO severity score) from Day 1 through Day 14. If a subject is discharged prior to Day 14, he/she will be assessed, if feasible, by phone daily through Day 14, and then at follow-up visits, on Days 28, 60, and 90, and as needed.

## **6.7. End of Study Definition**

End of study (EOS) will be defined as the date the last subject completes the EOS Visit (Day 90). The Sponsor will notify all applicable regulatory agencies in accordance with local requirements when the study has ended.

## **6.8. Criteria for Treatment Discontinuation**

Subjects are free to discontinue their participation in the study at any time and without prejudice to further treatment. The Investigator must withdraw any subject from the study if that subject requests to be withdrawn, or if it is determined that continuing in the study would result in a significant safety risk to the subject.

The subject's participation in this study may be discontinued for the following reasons:

- Subject withdrew consent
- Unacceptable AE
- Subject is unwilling or unable to continue the study or is lost to follow up
- Subject is non-compliant with study procedures/study protocol
- Investigator decides that withdrawal from the study is in the best interest of the subject
- Any clinically significant change in subject's medical condition (at the discretion of the Investigator)
- Sponsor decision to end the study

If a subject withdraws from the study prematurely, assessments scheduled for the EOS Visit should be performed ASAP. If a subject refuses further assessment, the subject should be contacted for safety evaluations (AE/concomitant medications/potential pregnancy) approximately 28 and 90 days after study withdrawal.

If such withdrawal occurs, or if the subject refuses to participate in the EOS Visit, the Investigator must determine the primary reason for a subject's withdrawal from the study and record the information on the electronic case report form (eCRF). If the reason for withdrawal is an AE, monitoring should continue until the outcome is evident. The specific event or test result(s) must be recorded in the eCRF. At the discretion of the Sponsor, subjects may also be removed from the study.

It should be clearly documented in the source data whether a subject withdrew his/her consent and will not enter the follow-up phase, or if a subject withdrew his/her consent for study drug treatment but will continue further participation in the study.

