### 5.2.2. Secondary Endpoints

- Safety and tolerability
  - Incidence, causality, and severity of AEs (graded according to the National Cancer Institute [NCI] Common Terminology Criteria for Adverse Events [CTCAE] version 5.0) in rhu-pGSN vs placebo groups
  - Frequencies of new or worsening clinically significant laboratory abnormalities in rhu-pGSN vs placebo groups
  - Mortality rate irrespective of cause at Days 28 and 90
- Efficacy
  - Daily change in 9-point WHO severity score through at least Day 14 (including after discharge, where feasible)
  - All-cause mortality at Days 28 and 90; time to death (Kaplan-Meier survival analysis)
  - Proportion of subjects alive on Days 7, 14, 28, 60, and 90 without:
    - Ongoing use of vasopressors
    - Ongoing intubation/mechanical ventilation
    - Ongoing residence in an ICU
    - New ongoing need for dialysis/renal replacement therapy (RRT)
  - Proportion of subjects discharged to home or immediate prior residence by Day 28
  - Days on the ventilator
  - Length of stay (LOS) in hospital and in ICU (days)
  - Re-admission to an acute-care hospital up to Day 90
- PK
  - PK for rhu-pGSN including maximum concentration ( $C_{max}$ ), time to maximum concentration ( $T_{max}$ ), terminal half-life ( $T_{1/2}$ ), area under the curve from time zero to 8 hours ( $AUC_{0-8}$ ), area under the curve from time 0 to infinity ( $AUC_{inf}$ ) for Dose #1 within 15 minutes predose, and at 1 ( $\pm 15$  min), 2 ( $\pm 15$  min), 6 ( $\pm 30$  min), and 12 ( $\pm 30$  min) hours after end of administration (but prior to Dose #2); for Dose #3 within 15 minutes predose, and at 1 ( $\pm 15$  min), 2 ( $\pm 15$  min), 6 ( $\pm 30$  min), 12 ( $\pm 30$  min) and 24 ( $\pm 30$  min) hours after the end of administration (participants refusing these blood samplings can enter and remain in the trial).
- Immunogenicity
  - Presence of anti-pGSN antibodies on Days 1 (predose), 28, and 90

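### Protocol 6.8 lets its treatment-discontinuation reasons end study participation after a 36-hour treatment, and requires no on-schedule outcome status from subjects who leave

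*Protocol*

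**What the plan says.** Protocol 6.5: "Subjects will be treated with 3 doses over 36 hours", with safety and efficacy follow-up through Day 90.

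Protocol 6.8 carries a treatment-discontinuation heading, but its operative sentence is "The subject's participation in this study may be discontinued for the following reasons". The list covers withdrawn consent, unacceptable AE, unwillingness or loss to follow-up, non-compliance, the investigator's view of the subject's best interest, a clinically significant change in condition, and sponsor decision. Before the list, the section makes withdrawal mandatory on the subject's request or for a significant safety risk.

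After exit: "If a subject withdraws from the study prematurely, assessments scheduled for the EOS Visit should be performed ASAP". For a subject who refuses further assessment, the fallback is that "the subject should be contacted for safety evaluations (AE/concomitant medications/potential pregnancy) approximately 28 and 90 days after study withdrawal". The last paragraph asks sites to record whether a subject withdrew consent altogether or only for study drug while staying in the study.

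The analysis rules that apply to leavers are:
- SAP 11.5 maps the same reasons to early termination from the study and keeps early-withdrawal results apart from the end-of-study results.
- Protocol 11.1 counts non-completers as failures. SAP 12.9.1.1 does the same for early discontinuation at Day 14, and SAP 12.9.2.3 at Days 7, 14, 28, 60 and 90.
- SAP 10.6 requires Day 14 completion and all three doses for the per-protocol set.
- SAP 11.18 censors time to death at withdrawal or last visit, whichever is earlier.

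**The concern.** Dosing is complete at 36 hours and the primary endpoint is read at Day 14. After Dose 3 there is no treatment left to stop, so ending participation for an AE, non-compliance or a change in condition protects nobody from further drug and only gives up follow-up. The one described route for stopping drug and staying in the study is worded for withdrawal of consent to the drug. A subject taken off drug by the investigator has no matching sentence.

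What is lost is outcome data that could often still be observed. In the FAS the subject becomes a failure whatever the true Day 14 status. In the per-protocol set the subject disappears. In the survival analysis, a subject who leaves because of worsening may be censored shortly before death, which is informative censoring.

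**Working it through.** **1. The plan's own power figure.** Inputs (Protocol 11.2, Part 1): 20% against 5%, one-sided alpha 0.2, N=54. I read these as failure proportions, because treatment is expected to raise survival without support; power is the same for 80% against 95%. With z = 0.8416 and a pooled test,

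power = Φ{[Δ√n − z√(2p̄q̄)] / √(p₁q₁ + p₂q₂)}.

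At n = 27: (0.15 × 5.196 − 0.8416 × 0.4677) / 0.4555 = 0.847, so power is 80.1%. The minimum observed difference at 27 per arm is 8.4 points (20% against 11.6%). Both stated figures are reproduced. At the enrolled 30 per arm (Protocol 7.1), power is 82.6% and the minimum difference from 20% is 8.0 points.

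**2. When the fallback contacts fall.** For withdrawal on study Day d, the contacts are at about d+28 and d+90. Windows from Protocol Table 5: Day 14 is 12–16, Day 28 is 26–30, Day 60 is 58–62, Day 90 is 86–94. The word approximately is treated as exact.

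| d | d+28 | d+90 | Windows met |
|---|---|---|---|
| 2 | 30 | 92 | Day 28, Day 90 |
| 3 | 31 | 93 | Day 90 |
| 4 | 32 | 94 | Day 90 |
| 5 to 13 | 33 to 41 | 95 to 103 | none |

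The Day 14 and Day 60 windows are never met. Even on target, the listed content does not include ventilator, vasopressor, dialysis, ICU or residence status.

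**3. What other leavers provide.** The end-of-study assessments include the WHO score (Table 5), but they are done once, at exit. They give Day 14 status only if exit happens to fall then.

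**4. Possible size.** The documents give no withdrawal rate, so the rates below are assumptions. If a share d of an arm leaves before Day 14 independently of outcome and counts as failure, failure probability f becomes f + d(1 − f). At 5% in each arm: placebo 0.20 + 0.05 × 0.80 = 0.24; rhu-pGSN 0.05 + 0.05 × 0.95 = 0.0975. Then (0.1425 × 5.477 − 0.8416 × 0.5297) / 0.5200 = 0.644, so power is 74.0%.

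| Leave, placebo / rhu-pGSN | Failure, placebo / rhu-pGSN | Power, 30 per arm |
|---|---|---|
| 0 / 0 | 20% / 5% | 82.6% |
| 5% / 5% | 24% / 9.75% | 74.0% |
| 10% / 10% | 28% / 14.5% | 67.1% |
| 20% / 20% | 36% / 24% | 56.9% |
| 0 / 5% | 20% / 9.75% | 60.9% |
| 10% / 5% | 28% / 9.75% | 83.9% |

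The direction depends on which arm loses more. If every leaver would have failed anyway, the rule changes nothing. One subject is 1/30 = 3.3 points of a Part 1 arm.

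**The case against.** The strongest reply is that the protocol does not equate stopping drug with leaving. Section 6.3 lets dosing stop, and 6.4 stops or bars injections after reactions, without requiring study exit. Section 6.9 names missed doses separately from discontinuing, and SAP 10.6 lists Day 14 completion and full dosing as separate conditions. The 6.8 list is permissive, and its last paragraph is a documentation instruction that need not exclude other routes. WHO scores, including the worst grades, are collected daily through Day 14, so worsening patients are plainly expected to be followed. All of this stands. A reader might infer that Day 14 and later endpoints are not collected from anyone who stops drug; the documents do not say that.

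A reader might also infer that injection reactions would drive exits in one arm. Section 6.4 manages them by slowing, stopping or barring injections, and no grade calls for study exit.

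The 28- and 90-day contacts concern only withdrawn subjects who refuse further assessment. Section 6.8 also asks for monitoring of an AE that caused withdrawal until its outcome is evident, and Protocol 10.1.2 records SAEs for 90 days after the last dose. So some deaths after exit would be known. Neither provision supplies organ-support status at Day 14, and SAP 11.18 does not say whether a death recorded after withdrawal counts as an event.

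Finally, counting non-completers as failures is prespecified, and Protocol 6.9 replaces non-informative losses before Day 14. That rule is defensible when status is unknown. It is less so when status could have been obtained by a phone call, and replacement does not cover exits for AEs or worsening.

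**Conclusion.** The point holds as a gap in the text. Section 6.8 permits study exit for reasons that belong to stopping drug, does not expressly keep in follow-up those who stop for reasons other than withdrawn consent for drug, and requires no on-schedule vital or organ-support status after exit. The analysis rules then replace an outcome that might have been observed with failure or censoring. The contact arithmetic is firm, subject to reading approximately as exact, and applies to refusers who leave on Days 2 to 13.

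The size is not established. The fall from 82.6% to 74.0% or 67.1% assumes 5% or 10% loss in each arm, independent of outcome. A reader might set a three-subject imbalance (3/30 = 10 points) against the stated 8.4-point threshold. The documents do not support that as a finding: no imbalance is given, all three would have to be successes otherwise, and 8.4 points belongs to 27 per arm with placebo at 20%. The change is worth making because it is cheap and reduces informative missingness, not because a particular bias has been shown.

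**What to change.** In Protocol 6.8, separate stopping study drug from leaving the study, without changing any ground for stopping drug. State that subjects who stop drug continue all scheduled assessments to Day 90 unless they withdraw consent for follow-up. Keep the mandatory safety withdrawal in 6.8 and the unblinding provision in 8.12.1, and reconcile both with the new text.

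For subjects who leave, time contacts from Dose 1 on Days 14, 28 and 90. Collect vital status, ventilator, vasopressor and dialysis use, and hospital and ICU status, by phone or record check where consent allows.

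Amend SAP 11.18, 12.9.1.1 and 12.9.2.3 so that observed status is used, with failure or censoring applied only when status is unknown. Align the non-completer sentence in Protocol 11.1 and the synopsis. Without these edits the newly collected data would not enter the main analyses.

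Cost: protocol wording, one extra contact for the few who leave before Day 14, a short eCRF page and a small SAP edit.
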